7.5 Efficacy

7.5.1 Primary Efficacy Analysis

SVI derived from the velocity time integral at the left ventricular outflow tract (LVOT VTI) at the end of the 5-hours infusion of treatment will be summarized descriptively for all randomized subjects by treatment group.

SVI will be assessed using a contrast comparing placebo and BMS-986231. We follow the linear model proposed by Jemielita et al³, which includes sequence and treatment and the difference in the treatment period baselines as a covariate. Jemielita et al demonstrated that modelling certain linear combinations of baseline values as covariates increases the power of the test for a difference in outcomes by treatment. In this study, the difference in baseline values among the treatments being compared will be considered according to this strategy. They further demonstrated that the model will give equivalent inference as in an ordinary least squares (OLS) model for difference of treatment effects, under the assumption of unstructured covariance structure. The Kenward-Roger approximation for the degrees of freedom will be specified for the model.

Estimation of the variance covariance will be based on unstructured (UN) R matrix assuming no common variances or covariances.

Let

$$X_{ik} = (X_{iPk}, X_{iNk}, X_{iTk})^T$$

$$Y_{ik} = (Y_{iPk}, Y_{iNk}, Y_{iTk})^T$$

be distinct 3-length vectors of baseline SVI and end of infusion SVI, respectively. The subscript $i=1, \dots, 6$ indexes the sequences, and P, N, T represent Placebo, NTG and BMS 986231. Moreover, $k=1, \dots, 7$ indexes subject k in sequence i .

We fit the following linear mixed model:

$$(Y_{iTk} - Y_{iPk}) | (X_{iTk} - X_{iPk}) = (\tau_T - \tau_P) + (\gamma_{iT} - \gamma_{iP}) + (\beta_T - \beta_P)(X_{iTk} - X_{iPk}) + (\varepsilon_{iTk} - \varepsilon_{iPk}),$$

where $\tau_T - \tau_P$ is the difference of treatment effects of BMS-986231 and Placebo, $\gamma_{iT} - \gamma_{iP}$ is the difference of treatment effect of BMS-986231 and Placebo within sequence i , $\beta_T - \beta_P$ is the regression coefficient, and $\varepsilon_{iTk} - \varepsilon_{iPk}$ is the variance term.

The hypotheses of interest are:

$$H_0: \tau_T - \tau_P = 0$$

$$H_A: \tau_T - \tau_P \neq 0.$$

The mean SVI at the end of 5-hour infusion of BMS-986231 versus Placebo, corresponding standard error, p value, and 95% confidence interval will be calculated by the below SAS code and presented. Considering the sample size is small, the Kenward-Roger degree of freedom is used to adjust the standard error of treatment effect.

```
PROC MIXED DATA=EXAMPLE_DATA;
  CLASS sequence;
  MODEL ydiff TP = sequence xdiff TP / DDFM=KENWARDROGER;
  ESTIMATE 'tau_T - tau_P' intercept 1 xdiff_TP / CL;
  run;
```

SVI will be summarized and listed for all randomized subjects as overall and by treatment.

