5.2 Number of Participants

Sample size calculations assume an increase of the stroke volume index (SVI) of 4.5 mL/m² from baseline, relative to placebo, an inter-individual SD of 10 mL/m², and intra-individual correlations for the difference between assessments of 0.7. Approximately 36 subjects with data from treatment periods being compared will be required to achieve a power of 90%, with a type I

error probability of 0.05 (2-sided). In order to address the potential for missing data arising from withdrawal from the study and/or losses to follow-up, an allowance of approximately 15% subjects will be included, with a resulting target sample size of 42 subjects to be randomized. An estimated 42 subjects will be randomized, in order to complete the study with 36 subjects. Further details are provided in [Section 10](#).

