10 STATISTICAL CONSIDERATIONS

10.1 Sample Size Determination

Based on a review of stroke volumes and stroke volume indices from the literature^{36,37}, baseline stroke volume index generally ranged from 30-40 mL/m², with inter-individual SD of approximately 25 – 35% of the mean. Likewise, SV values generally ranged from 50-70 mL, with inter-individual SD of approximately 25 – 35% of the mean. Results from these studies also suggest intra-individual correlations in the range of 0.6 – 0.8.

Sample size calculations assume baseline SVI of approximately 30 mL/m², with placebo values consistent with baseline, an increase of 15% from baseline, relative to placebo, as meaningful (e.g. 4.5 mL/m²), an inter-individual SD of 10 mL/m², and intra-individual correlations for the difference between placebo and HNO of 0.7. Using these assumptions, approximately 36 subjects with data from treatment periods being compared will be required to achieve a power of 90%, with a type I error probability of 0.05 (2-sided). In order to address the potential for missing data arising from dropout, an allowance of 15% subjects will be included, with a resulting target sample size of 42 subjects to be randomized. Sample sizes are calculated based on method IV from Mehrotra³⁸, which compares post baseline values, adjusting for the differences in the baseline value.

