10.3 Statistical Analyses

The statistical analysis plan will be developed and finalized before database lock and will describe the selection of participants to be included in the analyses, and procedures for accounting for missing, unused, and spurious data. Below is a summary of planned statistical analyses of the primary and secondary endpoints. For analyses involving baseline, the baseline value is defined by the last value prior to the start of infusion for a specified period, unless otherwise noted.

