10.3.1 Efficacy Analyses

Endpoint	Statistical Analysis Methods
Primary	Stroke volume index derived from the left ventricular outflow tract (LVOT) Doppler echocardiogram will be assessed using a contrast comparing placebo and BMS-986231 from a mixed model repeated measures (MMRM) analysis, with sequence, treatment period, and treatment, and the difference in the treatment period baselines as a covariate ³⁹ . The Kenward-Roger approximation for the degrees of freedom will be specified for the model. Estimation of the variance covariance will be based on unstructured (UN) R matrix assuming no common variances or covariances.
Secondary	Analyses of secondary endpoints will use a similar model as for the primary endpoints. For comparisons with NTG, the contrast and covariates will refer to values from the treatment periods using NTG and BMS-986231. No adjustments will be made for multiple comparisons.

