6.3 Populations for Analyses

The following populations will be used for the analyses:

- **The Enrolled Population** will consist of all subjects who sign informed consent
- **The Randomized Population** will consist of all randomized subjects who have started study drug infusion in at least one treatment period. This is also known as the Intent to Treat (ITT) population. Data in this data set will be analyzed based on randomized treatments in each period.
- **The Safety Population** will consist of all subjects who take at least 1 dose of double-blind study treatment. Participants will be included in the treatment group they received in each period.
- **The Pharmacokinetic analysis dataset (PK Population)** will consist of all subjects who receive BMS-986231 and have at least one post dose PK sample. Additionally, **the Evaluable PK Population** is defined as subjects who have adequate PK profiles.

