8.2 Baseline Measurements

For analyses involving baseline, the baseline value is defined by the last value prior to the start of infusion, unless otherwise noted.

When there is a missing baseline assessment it will not be imputed.

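### Does the primary SVI model's unstated restriction to complete BMS-986231/placebo pairs, with no missing-data sensitivity analysis, call for a change?

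*SAP*

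**What the plan says.** - **Model.** SAP 7.5.1 sets out a linear model "which includes sequence and treatment and the difference in the treatment period baselines as a covariate". It takes the BMS-986231-minus-placebo difference in end-of-infusion SVI as outcome and the matching baseline difference as covariate. The code is "MODEL ydiff TP = sequence xdiff TP / DDFM=KENWARDROGER", one row per subject. Protocol 10.3.1 describes a repeated-measures model "with sequence, treatment period, and treatment, and the difference in the treatment period baselines as a covariate". The SAP states that the two forms give equivalent inference under an unstructured covariance.
- **Population.** SAP 6.3 defines the Randomized (ITT) population as "all randomized subjects who have started study drug infusion in at least one treatment period".
- **Missing data.** Protocol 10.3 says the SAP will describe "procedures for accounting for missing, unused, and spurious data". For SVI, the only visible rule is in SAP 8.2: "When there is a missing baseline assessment it will not be imputed". Section 7.5.1 runs straight into 7.5.2 with no sensitivity analysis.
- **Sample size.** Protocol 10.1: "approximately 36 subjects with data from treatment periods being compared will be required to achieve a power of 90" per cent. Protocol 5.2 adds, for the "potential for missing data arising from withdrawal from the study and/or losses to follow-up, an allowance of approximately 15% subjects will be included", giving 42 randomized. SAP 2.2 does not replace those who discontinue.
- **Planned output.** SAP 7.3 summarizes non-completion of each infusion and of the study, with reasons. SAP 7.4 summarizes and lists interruptions, reductions and discontinuations by treatment. SAP 7.5.1 summarizes and lists SVI for all randomized subjects.

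**The concern.** A subject lacking any one of four SVI values has no row in the primary model, although the population section suggests that everyone who started an infusion counts. The SVI tables and the primary test can therefore rest on different subjects, and no analysis section says so. If subjects who respond poorly to BMS-986231 tend to leave before their placebo period, those who remain are a favourable selection. The estimated difference would then be too large and the type I error above 5%. With about 6 of 42 subjects (14%) expected to lack a pair and no replacement, this deserves a check.

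**Working it through.** **1. What forces pairs.** The outcome is itself a difference, so a subject missing either end-of-infusion value is lost whatever the covariate. The baseline difference adds the requirement for both baselines. In the protocol's form, a subject with both baselines and only one end value could still contribute. With a whole period missing, neither form can use the subject.

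**2. The plan's sample size.** Inputs (Protocol 10.1, SAP 5): difference 4.5, SD 10, correlation 0.7, two-sided 0.05, power 90%.

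- SD of the paired difference = 10 × √(2 × (1 − 0.7)) = 7.746.
- Normal approximation: n = (1.960 + 1.282)² × 7.746² / 4.5² = 31.1, so 32.
- Noncentral t, allowing for six sequences and the covariate (7 parameters): 34 pairs. The plan states 36, where power is 0.920.
- Allowance: 36 × 1.15 = 41.4, so 42.

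The 36 is thus a count of complete pairs, as the model requires. Power by number of pairs, same inputs:

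| Pairs | 42 | 36 | 34 | 32 | 30 | 28 |
|---|---|---|---|---|---|---|
| Power | 0.955 | 0.920 | 0.904 | 0.884 | 0.861 | 0.834 |

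Up to 8 of 42 pairs (19%) can be lost with power still at 90%. Suppose, beyond 15% dropout, that each echocardiogram is independently unusable with probability 1%, 2%, 3% or 5% (assumed rates). Then 42 × 0.85 × (1 − p)⁴ gives about 34, 33, 32 or 29 pairs, with power about 0.90, 0.89, 0.88 or 0.85.

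**3. Bias from the pairs lost.** The documents do not say why pairs will be missing, so a range is needed. Assumptions: 42 subjects, 7 per sequence; SD 10; cross-period correlation 0.7; same-period correlation 0.7 or 0.8; true difference 0; six pairs lost (6.3 on average in the logistic case); 10,000 datasets per cell; equal weights over sequences. Each cell shows bias in mL/m² and type I error.

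| Why pairs are lost | Correlation 0.7 | Correlation 0.8 |
|---|---|---|
| At random | +0.01, 5.6% | +0.01, 5.5% |
| Same rule after both treatments | −0.01, 5.4% | −0.01, 5.2% |
| Logistic withdrawal on SVI change, after BMS-986231 only | +0.47, 6.4% | +0.51, 6.8% |
| Three of six are the lowest SVI changes, BMS-986231 before placebo | +0.49, 7.0% | +0.53, 7.6% |
| All six are | +0.92, 10.4% | +0.99, 12.5% |

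The last row is 0.92/4.5 = 20% to 0.99/4.5 = 22% of the target. It removes exactly the six lowest responders among the 21 subjects given BMS-986231 before placebo (29%), with no pair lost for any other reason. The sign reverses if high responders leave.

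A separate large-sample run with a true difference of 4.5, 12 to 18% dropout and withdrawal driven by the SVI level gave pair estimates of 4.3 to 4.7, with simulation error about 0.1. When dropout was random at 15%, only 12.7% of pairs were lost, because leaving before a final NTG period costs no BMS-986231/placebo pair.

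**4. Would an all-data model do better?** The natural addition is a repeated-measures model of all six SVI values with unstructured covariance: 6 × 7 / 2 = 21 covariance parameters from 42 subjects. Its bias stays within 0.05 mL/m² in the random, three-of-six and all-six cases, and its SD is 4 to 8% larger than that of the pair model. However, its unadjusted standard error averages 1.04 to 1.15 against a true SD of 1.30 to 1.48. Its type I error with t(30) is about 9 to 13%, by maximum likelihood or REML, even when loss is random. That is as bad as the pair model's worst case, and it appears where the pair model is sound.

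**The case for a change.** The strongest case for acting is that the restriction is mechanical, is stated in no analysis section, and recurs for every secondary endpoint and for NTG, each with its own set of pairs. Protocol 10.3 promised missing-data procedures, which the SAP gives for safety dates and PK values but not for SVI. The disposition tables would not show a subject who completed every infusion but had an unreadable echocardiogram. Counting pairs in the sample size protects power but says nothing about who is lost.

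The omission is real. The protocol and SAP forms also differ slightly in whom they keep, and the SAP's sentence on an unstructured R matrix has no role in one-row-per-subject code. The inference that the result is at risk does not follow. Withdrawal could well be more frequent after a vasodilator than after placebo, but that causes bias only if those who leave also have unusual SVI changes. Under Protocol 7.4, infusion changes follow blood pressure and symptoms, end-of-infusion procedures are still done after a stop, and subjects stay eligible for later periods. A core lab analyses all echocardiograms and treatment is double-blind. No passage links leaving to SVI change. Parts of the SAP are removed or blacked out (the numbering jumps from 7.6.9 to 7.8), so a further analysis cannot be ruled out.

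**Conclusion.** No change is called for. The primary model uses complete BMS-986231/placebo pairs because its outcome is a within-subject difference. The formula and code leave an analyst no choice about this, and the sample size was built on it. At the plan's inputs, the result has 92% power with 36 pairs.

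The possible bias is about zero under random or treatment-neutral loss. It is about 0.5 mL/m² if withdrawal after BMS-986231 alone depends moderately on SVI change, and about 1 mL/m² in a contrived extreme. These figures rest on the assumed correlations, on six missing pairs and on withdrawal rules that the documents do not support.

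What remains is a gap that analysts fill as a matter of course: naming the model set and reporting how many subjects fall outside it. The planned disposition, exposure and SVI listings already hold most of what is needed. An all-data model would leave the primary result unchanged. It would need adjusted standard errors and a simpler covariance before anyone could rely on it at this sample size, so adding it is a matter of preference.

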7.5.2 Secondary Efficacy Analysis

Using the same model as in the primary analysis, this analysis will be repeated for the secondary endpoints listed below and will also examine the comparison of BMS-986231 vs NTG in addition to BMS-986231 vs Placebo.

- Mean SVI derived from LVOT VTI at the end of the 5-hours infusion of BMS-986231, versus NTG.
- Mean LVEF, computed by Simpson's method at the end of the 5-hours infusion of BMS-986231, versus placebo and NTG.
- Mean cardiac power index (CPI) at the end of the 5-hours infusion of BMS-986231, versus placebo and NTG. Cardiac power index is calculated by the following equation: CPI [W/m²] = mean aortic pressure [mmHg] × cardiac output [L/min] / body surface area [m²] × 0.0022.
- Mean Diastolic indices: E/A, annular e' velocity, and E/e' ratio at the end of the 5-hours infusion of BMS-986231, versus placebo and NTG.
- Mean LV global longitudinal strain, computed using STE at the end of the 5-hours infusion of BMS-986231, versus placebo and NTG.

The secondary endpoints will be summarized and listed for all randomized subjects as overall and by treatment.

7.6 Safety

All safety presentations will be based on the Safety Population.

7.6.1 Deaths

All reported deaths after a subject is enrolled (i.e., has signed the informed consent) will be listed separately by subject.

7.6.2 *Serious Adverse Events*

All reported serious adverse events (SAEs) will be listed by System Organ Class (SOCs) and Preferred Terms (PTs) for all safety population subjects. SAEs must be collected from the date of informed consent and will be assessed up to 30 days after the end of infusion of the last period.

7.6.3 *Adverse Events*

All AEs will be coded and grouped into PT by SOC, using current version of Medical Dictionary for Regulatory Activities (MedDRA). All recorded AEs will be summarized and listed by SOCs, PTs and treatment group.

Non-serious AEs with onset time from the start of study drug infusion, until 24 hours after end of infusion in each treatment period of dosing in each period will be included in the summary tables. Events will be assigned to the study treatment administered to the subject. The proportion of subjects having an adverse event will be calculated as the number of subjects experiencing the event, divided by the total number of subjects receiving study treatment.

All AE listings will indicate the unique subject identifier, age, gender, current treatment, the date and time of onset, the date and time of resolution, day of onset relative to the start of treatment, action taken, investigator's assessment of severity and relationship to study drug. Additional listings will be provided for adverse events leading to discontinuation and adverse events without recorded resolution. Summaries of adverse events will include adverse events, adverse events by intensity and adverse events by relationship.

Where a subject has the same adverse event, based on preferred terminology, reported multiple times in a single analysis period, the subject will only be counted once at the preferred terminology level in adverse event frequency tables.

Where a subject has multiple adverse events within the same system organ class in a single analysis period, the subject will only be counted once at the system organ class level in adverse event frequency tables.

When a subject has the same adverse event, based on preferred terminology, reported multiple times in a single analysis period, the following criteria, in order of precedence, will be used to select the event to be included in summary tables:

- Relationship to study medication
- Intensity of event
- Onset date and time

When reporting adverse events by intensity, in addition to providing a summary table based on the event selection criteria detailed above, summary tables will also be provided based on the most intense event during the analysis period - independent of relationship to study medication. For these tables, the following criteria, in order of precedence, will be used to select the event to be included in summary tables:

- Intensity of event

- Onset date and time

Subjects will only be counted once in the ‘Total’ at their maximum intensity, regardless of SOC or PT.

7.6.4 Clinical Laboratory Evaluations

The results of all protocol-specified clinical laboratory tests will be listed. Scheduled laboratory measurements will be summarized by treatment and scheduled time points for each laboratory test.

The criteria used for classifying laboratory test results as markedly abnormal will be listed.

Laboratory results for subjects with any marked laboratory abnormality (scheduled and unscheduled) will be listed. This listing will include all observations for the specific laboratory test and subject, not only the marked laboratory abnormalities. The frequency of subjects with any marked laboratory abnormality as well as hematology, serum chemistry, and urinalysis marked abnormalities, based on pre-specified criteria (see Table 6.6.2.4-1), will be presented.

Troponin T will be summarized descriptively by treatment for each time point, as well as change from baseline. Geometric mean and coefficient of variation (%CV) will also be presented for the original values and percent of baseline.

Table 6.6.2.4-1: Laboratory MA Criteria

Parameter	Test Code	Direction of Change	MA Criteria in US Standard Units (apply to labs collected after baseline only)	MA Criteria in SI Units (apply to labs collected after baseline only)
HEMATOLOGY				
Hemoglobin	HB	Low only	> 2 g/dl decrease compared to pre-dose or Value \leq 8 g/dl	> 20 g/l decrease compared to pre-dose or Value \leq 80 g/l
Hematocrit	HCT	Low only	< 0.75 \times pre-dose	< 0.75 \times pre-dose
Erythrocytes	RBC	Low only	< 0.75 \times pre-dose	< 0.75 \times pre-dose
Platelet Count	PLAT	Low Only	< 100,000/mm ³ (or < 100 \times 10 ⁹ cells/L)	< 100 \times 10 ⁹ cells/L
Leukocytes	WBC	Low/High	< 0.75 \times LLN or > 1.25 \times ULN, or if pre-dose < LLN then use < 0.8 \times pre-dose or > ULN if pre-dose > ULN then use > 1.2 \times pre-dose or < LLN	< 0.75 \times LLN or > 1.25 \times ULN, or if pre-dose < LLN then use < 0.8 \times pre-dose or > ULN if pre-dose > ULN then use > 1.2 \times pre-dose or < LLN
Neutrophils (absolute)	NEUTA	Low Only	< 1.0 \times 10 ³ cells/ μ L	< 1.0 \times 10 ⁹ cells/L
LIVER/KIDNEY				
Alkaline Phosphatase	ALP	High only	> 2 \times ULN	> 2 \times ULN
Aspartate	AST	High only	> 3 \times ULN, > 5 \times ULN, > 10 \times ULN	> 3 \times ULN, > 5 \times ULN, > 10 \times ULN

Table 6.6.2.4-1: Laboratory MA Criteria

Parameter	Test Code	Direction of Change	MA Criteria in US Standard Units (apply to labs collected after baseline only)	MA Criteria in SI Units (apply to labs collected after baseline only)
Aminotransferase				
Alanine Aminotransferase	ALT	High only	$> 3 \times \text{ULN}$, $> 5 \times \text{ULN}$, $> 10 \times \text{ULN}$	$> 3 \times \text{ULN}$, $> 5 \times \text{ULN}$, $> 10 \times \text{ULN}$
Bilirubin, Total	TBILI	High only	$> 2 \times \text{ULN}$	$> 2 \times \text{ULN}$
Blood Urea Nitrogen	BUN	High only	$> 2 \times \text{ULN}$	$> 2 \times \text{ULN}$
Serum Creatinine	CREAT	High only	$> 1.5 \times \text{ULN}$	$> 1.5 \times \text{ULN}$
ELECTROLYTES				
Sodium, Serum	NA	Low/High	$< 0.95 \times \text{LLN}$ or $> 1.05 \times \text{ULN}$, or if pre-dose $< \text{LLN}$ then use $< 0.95 \times \text{pre-dose}$ or $> \text{ULN}$ if pre-dose $> \text{ULN}$ then use $> 1.05 \times \text{pre-dose}$ or $< \text{LLN}$	$< 0.95 \times \text{LLN}$ or $> 1.05 \times \text{ULN}$, or if pre-dose $< \text{LLN}$ then use $< 0.95 \times \text{pre-dose}$ or $> \text{ULN}$ if pre-dose $> \text{ULN}$ then use $> 1.05 \times \text{pre-dose}$ or $< \text{LLN}$
Potassium, Serum	K	Low/High	$< 0.9 \times \text{LLN}$ or $> 1.1 \times \text{ULN}$, or if pre-dose $< \text{LLN}$ then use $< 0.9 \times \text{pre-dose}$ or $> \text{ULN}$ if pre-dose $> \text{ULN}$ then use $> 1.1 \times \text{pre-dose}$ or $< \text{LLN}$	$< 0.9 \times \text{LLN}$ or $> 1.1 \times \text{ULN}$, or if pre-dose $< \text{LLN}$ then use $< 0.9 \times \text{pre-dose}$ or $> \text{ULN}$ if pre-dose $> \text{ULN}$ then use $> 1.1 \times \text{pre-dose}$ or $< \text{LLN}$
Chloride, Serum	CL	Low/High	$< 0.9 \times \text{LLN}$ OR $> 1.1 \times \text{ULN}$, or if pre-dose $< \text{LLN}$ then use $< 0.9 \times \text{pre-dose}$ or $> \text{ULN}$ if pre-dose $> \text{ULN}$ then use $> 1.1 \times \text{pre-dose}$ or $< \text{LLN}$	$< 0.9 \times \text{LLN}$ OR $> 1.1 \times \text{ULN}$, or if pre-dose $< \text{LLN}$ then use $< 0.9 \times \text{pre-dose}$ or $> \text{ULN}$ if pre-dose $> \text{ULN}$ then use $> 1.1 \times \text{pre-dose}$ or $< \text{LLN}$
Calcium, Total	CA	Low/High	$< 0.8 \times \text{LLN}$ or $> 1.2 \times \text{ULN}$, or if pre-dose $< \text{LLN}$ then use $< 0.75 \times \text{pre-dose}$ or $> \text{ULN}$ if pre-dose $> \text{ULN}$ then use $> 1.25 \times \text{pre-dose}$ or $< \text{LLN}$	$< 0.8 \times \text{LLN}$ or $> 1.2 \times \text{ULN}$, or if pre-dose $< \text{LLN}$ then use $< 0.75 \times \text{pre-dose}$ or $> \text{ULN}$ if pre-dose $> \text{ULN}$ then use $> 1.25 \times \text{pre-dose}$ or $< \text{LLN}$
Bicarbonate	HCO3	Low/High	$< 0.75 \times \text{LLN}$ or $> 1.25 \times \text{ULN}$, or if pre-dose $< \text{LLN}$ then use $< 0.75 \times \text{pre-dose}$ or $> \text{ULN}$ if pre-dose $> \text{ULN}$ then use $> 1.25 \times \text{pre-dose}$ or $< \text{LLN}$	$< 0.75 \times \text{LLN}$ or $> 1.25 \times \text{ULN}$, or if pre-dose $< \text{LLN}$ then use $< 0.75 \times \text{pre-dose}$ or $> \text{ULN}$ if pre-dose $> \text{ULN}$ then use $> 1.25 \times \text{pre-dose}$ or $< \text{LLN}$
OTHER CHEMISTRY				
Creatine Kinase	CK	High only	$> 5 \times \text{ULN}$	$> 5 \times \text{ULN}$

Table 6.6.2.4-1: Laboratory MA Criteria

Parameter	Test Code	Direction of Change	MA Criteria in US Standard Units (apply to labs collected after baseline only)	MA Criteria in SI Units (apply to labs collected after baseline only)
Total Protein	TPRO	Low/High	< 0.9 × LLN or > 1.1 × ULN, or if pre-dose < LLN then use 0.9 × pre-dose or > ULN if pre-dose > ULN then use 1.1 × pre-dose or < LLN	< 0.9 × LLN or > 1.1 × ULN, or if pre-dose < LLN then use 0.9 × pre-dose or > ULN if pre-dose > ULN then use 1.1 × pre-dose or < LLN
Glucose, Serum Fasting	GLUCF	Low/High	< 0.8 × LLN or > 1.5 × ULN, or if pre-dose < LLN then use < 0.8 × pre-dose or > ULN if pre-dose > ULN then use > 2.0 × pre-dose or < LLN	< 0.8 × LLN or > 1.5 × ULN, or if pre-dose < LLN then use < 0.8 × pre-dose or > ULN if pre-dose > ULN then use > 2.0 × pre-dose or < LLN
Uric Acid	URIC	High only	> 1.5 × ULN, or if pre-dose > ULN then use > 2 × pre-dose	> 1.5 × ULN, or if pre-dose > ULN then use > 2 × pre-dose
Albumin		Low only	≤ 2 g/dL	≤ 20 g/L

URINALYSIS

Protein, Urine	UPRO	High only	If missing pre-dose then use ≥ 2, or if value ≥ 4, or if pre-dose = 0 or 0.5 then use ≥ 2, or if pre-dose = 1 then use ≥ 3, or if pre-dose = 2 or 3 then use ≥ 4	If missing pre-dose then use ≥ 2, or if value ≥ 4, or if pre-dose = 0 or 0.5 then use ≥ 2, or if pre-dose = 1 then use ≥ 3, or if pre-dose = 2 or 3 then use ≥ 4
Blood, Urine	UBLD	High only	If missing pre-dose then use ≥ 2, or if value ≥ 4, or if pre-dose = 0 or 0.5 then use ≥ 2, or if pre-dose = 1 then use ≥ 3, or if pre-dose = 2 or 3 then use ≥ 4	If missing pre-dose then use ≥ 2, or if value ≥ 4, or if pre-dose = 0 or 0.5 then use ≥ 2, or if pre-dose = 1 then use ≥ 3, or if pre-dose = 2 or 3 then use ≥ 4
Leukocyte Esterase, Urine	ULEUK	High only	If missing pre-dose then use ≥ 2, or if value ≥ 4, or if pre-dose = 0 or 0.5 then use ≥ 2, or if pre-dose = 1 then use ≥ 3, or if pre-dose = 2 or 3 then use ≥ 4	If missing pre-dose then use ≥ 2, or if value ≥ 4, or if pre-dose = 0 or 0.5 then use ≥ 2, or if pre-dose = 1 then use ≥ 3, or if pre-dose = 2 or 3 then use ≥ 4
RBC, Urine	URBC	High only	If missing pre-dose then use ≥ 2, or if value ≥ 4, or if pre-dose = 0 or 0.5 then use ≥ 2, or	If missing pre-dose then use ≥ 2, or if value ≥ 4, or if pre-dose = 0 or 0.5 then use ≥ 2, or

Table 6.6.2.4-1: Laboratory MA Criteria

Parameter	Test Code	Direction of Change	MA Criteria in US Standard Units (apply to labs collected after baseline only)	MA Criteria in SI Units (apply to labs collected after baseline only)
			if pre-dose = 1 then use ≥ 3 , or if pre-dose = 2 or 3 then use ≥ 4	if pre-dose = 1 then use ≥ 3 , or if pre-dose = 2 or 3 then use ≥ 4
WBC, Urine	UWBC	High only	If missing pre-dose then use ≥ 2 , or if value ≥ 4 , or if pre-dose = 0 or 0.5 then use ≥ 2 , or if pre-dose = 1 then use ≥ 3 , or if pre-dose = 2 or 3 then use ≥ 4	If missing pre-dose then use ≥ 2 , or if value ≥ 4 , or if pre-dose = 0 or 0.5 then use ≥ 2 , or if pre-dose = 1 then use ≥ 3 , or if pre-dose = 2 or 3 then use ≥ 4

